13 INCLUSION CRITERIA

- 1. Females aged 18 to 65 years old inclusive
- 2. An adaption of Rome II criteria for functional constipation will be used. Eligible patients must have functional constipation for the previous three months with symptom onset at least six months prior to diagnosis with less than three complete spontaneous bowel movements per week with two or more of the following:
 - a. hard or lumpy stools at least 25 % of the time
 - b. straining during a bowel movement at least 25 % of the time
 - c. sensation of incomplete evacuation at least 25 % of the time
 - d. sensation of anorectal obstruction/blockage at least 25 % of the time
- 3. A normal rectal exam result on file within the past 2 years or performed at Visit 1 screen by a qualified gastroenterologist to exclude the possibility of an evacuation disorder. Examination must exclude findings suggestive of an evacuation disorder such as high sphincter tone at rest, failure of perineal descent and spasm, tenderness or paradoxical contraction of the puborectalis muscles.
- 4. Females of child-bearing potential (those who have not experienced a bilateral tubal ligation, hysterectomy or menopause) must use an acceptable method of contraception during the study. Acceptable methods are surgical sterilization, hormonal methods such as oral contraceptives, Norplant and Depo-Provera, double barrier method such as a condom and spermicide, and an IUD. Abstinent females may participate if they agree to use the double barrier method should they become sexually active during the study.
- 5. Able to provide written informed consent prior to any study procedures being performed

14 EXCLUSION CRITERIA

- 1. Female patients who are pregnant or breast feeding
- 2. Structural or metabolic diseases/conditions that affect the gastrointestinal system or functional gastrointestinal disorders other than constipation. The long version BDQ will be used to confirm patients have constipation.
- 3. Taking any medication that in the opinion of the principal investigator has a potential to alter GI transit. This includes but is not limited to osmotic or stimulant laxatives, magnesium or aluminum-containing antacids, prokinetics, erythromycin, narcotics, anticholinergics, selective norepinephrine reuptake inhibitors (SNRIs), opiates, GABAergic agents and benzodiazepines.

Note: Selective serotonin reuptake inhibitor (SSRI) antidepressants are permissible at low, stable doses. Analgesics such as Tylenol, ibuprofen, naproxen and aspirin are permissible. All medications shall be reviewed by the principal investigator on a case by case basis.

- 4. Clinical evidence (including but not limited to a clinically significant abnormal physical exam, ECG or laboratory test result in the past medical record) or current clinically significant abnormal physical exam or laboratory test result that could indicate significant cardiovascular, respiratory, renal, hepatic, gastrointestinal, hematological, neurological, psychiatric or other diseases that interfere with the objectives of the study. If a laboratory test result is abnormal and clinically significant, it may be repeated once at the discretion of the PI. If the laboratory test result remains abnormal and clinically significant, the patient will be discontinued from the study and referred to a primary care physician for further evaluation.
- 5. Patients who are considered by the PI to be alcoholics not in remission or known substance abusers.
- 6. Patients who have participated in another clinical study in the past 30 days.

15 GENDER/MINORITY MIX

We justify restricting enrollment to only female patients with functional constipation by the following:

- 1. The clinical population presenting with functional constipation is greater than 90 percent female.
- 2. The clinical population potentially receiving A3309 as a treatment for functional constipation is mostly female.
- 3. This is a non-therapeutic study; therefore, we are not depriving males of a potential therapy for functional constipation.

It is anticipated that the racial/ethnic characteristics of the group will reflect the communities in Olmsted County, Minnesota and are anticipated to be 90% Caucasian, 5% Asian and 5% other minorities. The prevalence of IBS among whites, blacks and Hispanics in the U.S. is very similar.

There are no known ethnic or gender differences in bioavailability of A3309. Hence, we anticipate the results of our study will be generalizable.

16 RESTRICTIONS

Patients must report to Charlton 7 CRU fasting for the previous eight hours for all study visits, Visits 1 to 7.

Rescue medications (Milk of Magnesia, Dulcolax and Fleets/tap water enemas) may be used but only under the direction of the PI. Rescue medications must not be used within the seven days prior to both the abbreviated and full transit scintigraphy tests. Since each patient's schedule will differ, each patient will be instructed as to when rescue medication may not be taken.

17 STUDY WITHDRAWAL

A study patient should be withdrawn from the study treatment if, in the opinion of the Investigator, it is medically necessary, or if it is the expressed wish of the patient.

Irrespective of the reason for withdrawal and whenever possible, the patient should be examined. Relevant laboratory test samples should be obtained and all relevant assessments should be completed, preferably according to the scheme for the final assessment. The CRF should be completed as far as possible and collected by the Monitor.

A withdrawn patient is not allowed to re-enter into the study.

18 SCREENING AND ENROLLMENT LOG

The site will keep a log of all patients screened and included. The reason for screen failure should be stated for all patients screened but not included. The reason for withdrawal should be stated for all patients included but not completed.

19 INVESTIGATIONAL PRODUCT

Investigational Product (IP) will be provided by Albireo. The study will be performed under an IND held by Albireo, IND number 103,060.

The active pharmaceutical ingredient (API) in A3309 is manufactured by Syngene as a white to off-white powder. The IP will be shipped from Galenica to the Mayo Research Pharmacy.

19.1 Packaging, labeling and storage of Investigational Product

The A3309 tablets will be delivered to the Mayo Research Pharmacy in aluminium sachets. The sachets are packed in HDPE containers (DUMA Twist-Off) with childproof polypropylene caps (DUMA Twist-Off cap).

The label of the sachets (primary container) will include:

Content: A3309 tablets and/or Placebo tablets

Protocol Number: A3309-003

Albireo 30(89) 07 June 2010

Storage: Room Temperature (preferably 20 – 25 °C)

Batch No: 96202-YYMM-XX Use by: YYYY-MM-DD

Caution: New drug - Limited by Federal (USA) Law to Investigational Use *Sponsor: Albireo AB, [name]*

Keep Out of Reach of Children.

Take both tablets orally daily before breakfast

The label of the HDPE containers (secondary container) will include:

18 sachets containing two tablets each.

Content: A3309 tablets and/or Placebo tablets

Protocol Number: A3309-003

Patient no: XXXX

Storage: Room Temperature (preferably 20 – 25 °C)

Batch No: 96202-YYMM-XX Use by: YYYY-MM-DD

Caution: New drug - Limited by Federal (USA) Law to Investigational Use *Sponsor: Albireo AB, [name]*

Manufactured by: Galenica AB, [name]

Clinical site: Mayo Clinics, xxxxxxxxxxx, phone: xxxxxx

Keep Out of Reach of Children.

Take both tablets from one sachet orally daily before breakfast.

19.2 Doses and treatment regimens

Patients will receive placebo or 15 mg or 20 mg A3309 tablets taken orally once daily for eleven consecutive days at home and once daily for three consecutive days of the final transit scintigraphy test at the Charlton 7 CRU. Study medication will be administered at Charlton 7 CRU by CRU nurses.

Based on the effect on the biomarker C4, data on colon transit, and results of patient-reported outcomes in study A3309-001, the protocol design includes two dose levels: 15 and 20 mg.

These dose estimations are based on the following findings from preclinical studies:

- PD effects of A3309 tested in several species in both *in vitro* and *in vivo* experiments. The *in vitro* potency in human IBAT-transfected cells, as well as the *in vitro* and *in vivo* potency in the mouse and the dog were used to approximate an effective dose in humans from 0.25 to 0.5 μmol/kg.
- A dose of A3309 0.16 μmol/kg resulted in twice the fecal excretion of ⁷⁵SeHCAT in the mouse than in humans over a 24-hour period; mouse IBAT showed a 3-fold greater potency than human IBAT. In the dog, a clear increase of C4 and in diarrhea was observed and a reversal of meatinduced constipation was detected at 5 μmol/kg (the canine IBAT has a 10-fold less potency than human IBAT). As diarrhea was observed in the dog at 5 μmol/kg in the 3 month toxicology study, this dose is probably too high for use in patients with constipation.
- Evaluation of the results of the A3309-001 study showed:

- A minor signal on C4 and on lipid parameters observed at the 3 mg and the 10 mg dose levels produced a stronger signal;
- Efficacy signals (colon transit, stool form scale (28), and frequency of BMs) evident in the 10 mg dose group. However, no diarrhea or incapacitating "very loose stools" were observed in the 10 mg dose group.

Given the paucity of data, the therapeutic oral dose range in man is difficult to estimate but may be in the range of 5 to 20 mg, as calculated from *in vitro* potency in human IBAT-transfected cells and from *in vitro* and *in vivo* potency in the mouse, dog, and man.

Previous experience with A3309 does not include dose levels greater than 10 mg. Evaluating 15 mg and a 20 mg dose level is adequate given:

- The large safety window in the preclinical toxicology package. The only dose-limiting effect identified was emesis in female dogs given high dose. The preliminary NOAEL in the rat was 350 mg/kg, 140 mg/kg in the male dog, and 17.5 mg/kg in the female dog, giving an approximate safety margins of approximately 520 to 1300-fold differences for a 20 mg dose (see Section 1.2.6).
- The extremely low systemic exposure (picomolar exposure) of both A3309 and its metabolites
- The high protein binding (approximately 99.5 %), and
- The benign safety profile in the Phase Ib study

The available toxicological documentation indicates that A3309 can be given orally to humans for up to 3 months duration at doses of 15 mg and potentially within the range of 1 to 20 mg for up to 90 days. In parallel with this study a Phase IIb study (A3309-002) is ongoing in the US including three dose levels (5, 10 and 15 mg) and with a treatment duration of 8 weeks. Based on the results of that study and the results of this study data will be evaluated and a decision taken whether to continue into a Phase 3 program.

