A3309 intravenously infused in the anesthetised dog at the doses of 0.0035, 0.035, 0.35, 3.5 mg/kg did not cause any pharmacologically relevant action on cardiovascular parameters. The only statistically significant change was a slight decrease in mean coronary blood flow and increase in coronary resistance. However, in the absence of any other hemodynamic effects, even at plasma concentration of 10,000 nmol/L, the effect on coronary flow is considered to be of no biological significance.

In addition, no cardiovascular effects were observed in the three-month toxicity study in dog at doses up to 140 mg/kg (520 times a human dose of 20 mg). A3309 had low effect *in vitro* in a variety of tissue models, enzyme/binding assay and on the hERG potassium channel; IC50 > 2000 fold higher than IC50 in the human IBAT transfected cell assay.

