In a one-month toxicity study in dogs, groups of 3 males and 3 females were given A3309 orally once daily for 28 days at 0, 3.5, 17 and 140 mg/kg/day. The only blood chemistry change considered

noteworthy at these dose levels was a slightly reduced level of plasma triglycerides. For all other parameters, including histopathology, there were no toxicologically significant, treatment-related changes. Based on the findings of emesis and soft/fluid feces at 17 and 140 mg/kg the NOAEL in dogs was considered to be 3.5 mg/kg/day. However, excluding these signs of mild gastrointestinal intolerance there were no effects of toxicological significance at doses up to and including 140 mg/kg.

In a three-month toxicity study in dogs, groups of 4 males and 4 females were given A3309 orally once daily for 13 weeks at 0, 3.5, 17.5 and 140 mg/kg/day. Dose related liquid feces were seen in all groups treated with A3309. An increase in liver weight and minor changes in red blood cell parameters at high dose was not considered toxicologically significant. NOAEL for males was 140 mg/kg/day but in females 17.5 mg/kg/day based upon emesis occurring at the higher dose.

Thus, the main target organ for A3309 in the toxicology studies appears to be the gastrointestinal tract. It is most likely that the effects seen in the gastrointestinal tract are related to the pharmacological activity of A3309, e.g. increased colon motility. Based on the available toxicological documentation, it is concluded that A3309 can be given orally to man up to three months of duration in the proposed clinical trials with sufficient safety.

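### The safety margin of 520 to 1300-fold for 20 mg in section 19.2 leaves out the female-dog NOAEL in its own sentence; on the same basis that NOAEL gives about 65-fold, and the trial enrolls only women

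*Combined protocol and SAP*

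**What the plan says.** Section 19.2 notes that experience with A3309 had not gone beyond 10 mg, and gives four reasons why 15 and 20 mg are adequate. The first is a large safety window in the preclinical toxicology. That paragraph says: "The only dose-limiting effect identified was emesis in female dogs given high dose". It then gives a rat NOAEL of 350 mg/kg, followed by "140 mg/kg in the male dog, and 17.5 mg/kg in the female dog", and closes with "giving an approximate safety margins of approximately 520 to 1300-fold differences for a 20 mg dose". The sentence does not say which NOAELs the range covers. As written, the range follows from all three.

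Two other places give the background. Section 8.3 mentions the three-month dog study "at doses up to 140 mg/kg (520 times a human dose of 20 mg"), which ties the 520 figure to 140 mg/kg. Section 8.6 reports that study by sex: "NOAEL for males was 140 mg/kg/day but in females 17.5 mg/kg/day based upon emesis occurring at the higher dose". The dose groups were 0, 3.5, 17.5 and 140 mg/kg/day, so the higher dose is 140 mg/kg.

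Inclusion criterion 1 in section 13 limits enrollment to females.

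**The concern.** A margin quoted as a range is normally read as running from the least to the most favorable of the inputs given. Here the lowest input is 8 times below the next one, yet the bottom of the range does not reflect it. In female dogs, 520-fold corresponds to 140 mg/kg, the dose at which the NOAEL-defining emesis occurred.

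The omission falls on the input closest to this trial. All patients are women, and emesis in female dogs is the one dose-limiting effect that the paragraph identifies. The range is also the only number that quantifies the safety window, which is the first reason offered for doubling the highest human dose given so far.

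**Working it through.** **Inputs.**
- NOAELs of 350, 140 and 17.5 mg/kg (section 19.2; the dog values by sex also in section 8.6).
- Human dose of 20 mg and stated margins of 520 and 1300 (section 19.2).
- 140 mg/kg in the dog equated with 520 times 20 mg (section 8.3).

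**Formula.** Margin = NOAEL in mg/kg ÷ (human dose in mg ÷ body weight in kg).

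**Step 1: reproduce the stated range.** The body weight is not given, so solve for it at each end.
- Male dog: 520 × 20 / 140 = 74.3 kg.
- Rat: 1300 × 20 / 350 = 74.3 kg.

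Both ends give the same weight. The range is therefore a plain mg/kg comparison for a person of about 74 kg, and 20 mg corresponds to 20 / 74.3 = 0.269 mg/kg. Check: 140 / 0.269 = 520 and 350 / 0.269 = 1300.

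**Step 2: apply the same basis to the third NOAEL.**
- Female dog: 17.5 / 0.269 = 65-fold.
- By proportion, with no body weight needed: 520 × 17.5 / 140 = 65, and 1300 × 17.5 / 350 = 65.

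**Step 3: size of the discrepancy.** 520 / 65 = 8, the same as 140 / 17.5. This ratio holds at any body weight.

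| NOAEL at 20 mg, 74.3 kg | mg/kg | Margin | In the stated range? |
|---|---|---|---|
| Rat | 350 | 1300 | Yes, upper end |
| Male dog | 140 | 520 | Yes, lower end |
| Female dog | 17.5 | 65 | No |

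**Step 4: sensitivity to body weight (assumed; the documents give no expected weight).**
- 60 kg: 17.5 × 60 / 20 = 52.5-fold.
- 80 kg: 17.5 × 80 / 20 = 70-fold.

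No weight in this range brings the female-dog margin near 520.

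**Step 5: the 15 mg dose, on the 74.3 kg basis.** 65 × 20 / 15 = 87-fold.

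**The case against.** **Nothing is hidden.** This stands. The 17.5 mg/kg figure is printed beside the 140 mg/kg figure, the emesis is named just before the range, and section 8.6 repeats both. A careful reader can see the eightfold gap. A reader might infer that the female finding was withheld, or that the ethics board was misled. The documents support neither, because what is wrong is the derived range and not the disclosure of its inputs. The sentence also points to a Section 1.2.6 that is not in this protocol's table of contents, so it cannot be checked whether a female margin is given there.

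**For effects other than emesis, 520-fold can be defended in females.** This also stands. The three-month female NOAEL rests on emesis, and the liver-weight and red-cell changes at the high dose were judged not toxicologically significant. For the one-month study, which used both sexes, section 8.6 says that "excluding these signs of mild gastrointestinal intolerance there were no effects of toxicological significance at doses up to and including 140 mg/kg". It would therefore be too strong to say that 520-fold means nothing for women. But the sentence does not restrict its range in that way, and it follows a statement that names emesis in females as the dose-limiting effect.

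**The true worst case might be thought lower still.** Section 8.6 says of the one-month study: "Based on the findings of emesis and soft/fluid feces at 17 and 140 mg/kg the NOAEL in dogs was considered to be 3.5 mg/kg/day". On the 74 kg basis, 3.5 mg/kg gives 3.5 / 0.269 = 13-fold. At three months, "Dose related liquid feces were seen in all groups treated with A3309". A reader might infer that 13-fold is the correct lower bound. The documents do not support that as a correction to this sentence, which does not cite the one-month NOAEL. Section 8.6 also attributes that NOAEL to mild gastrointestinal intolerance. Section 19.2 claims no margin for diarrhea. It already says that the dog dose of 5 μmol/kg (3.5 mg/kg by Table 2) is likely to be too high in constipation because of diarrhea.

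**The consequence is small.** Largely true, and reflected in the verdict.

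**Conclusion.** The stated range is wrong for the inputs listed with it. It should run from about 65 to 1300-fold, so the lower bound is overstated by a factor of 8. The 65-fold figure needs only the plan's own mg/kg basis. At assumed body weights of 60 to 80 kg it becomes 52.5 to 70-fold.

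These are ratios of dose per kilogram, as in the plan, and not ratios of exposure. Section 8.5 says that exposure in the dog rose less than in proportion at the highest doses, so the gap between 140 and 17.5 mg/kg may be smaller in exposure terms.

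A reader might infer that 20 mg is unsafe or that the dose choice fails. The documents do not support that. A margin of 65-fold for emesis is still sizeable. Section 19.2 bases the doses on C4, colon transit and patient-reported results from study A3309-001, and adds very low systemic exposure, high protein binding and the Phase Ib safety profile. This is an error in a safety figure that should be corrected, and not a fault in the design.

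**What to change.** In section 19.2, replace the range with: 'giving approximate safety margins for a 20 mg dose (about 74 kg) of 1300-fold in the rat, 520-fold in the male dog and 65-fold in the female dog (NOAEL based on emesis).'

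The cost is one sentence at the next amendment. Doses, visits, eligibility, sample size and analysis are unaffected. Two additions are optional and not part of the correction: the 13-fold figure from the one-month dog study, and a statement that no wide margin is claimed for diarrhea.

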19.3 Product accountability

The IP will be released to the study site after approvals of the study protocol have been received from the IRB and the Regulatory Authority. The IP will be stored at and dispensed by the Mayo Research Pharmacy and administered by the Charlton 7 CRU nurses.

The Mayo Research Pharmacy will be responsible for keeping detailed dispensation records, which show the quantity of IP that is stored, removed from the place of storage, prepared for delivery to Charlton 7 CRU and any unused product returned from Charlton 7 CRU. Any discrepancies between dispensed and returned IP must be explained and documented.

The CRU will keep record of IP administered to the patients.

IPs deliberately and/or accidentally destroyed by the Research Pharmacy or the dispensing nurses must also be accounted for.

The Monitor will perform IP accountability and make sure that all unused IP is adequately destroyed/returned and documented.

20 RANDOMIZATION METHODS

Randomization will be stratified on BMI ($< 25, > = 25 \text{ kg/m}^2$). IP doses will be randomly assigned in fixed block sizes according to a schedule provided by the study statistician. Mayo Clinic Research Pharmacy will maintain the randomization schedule.

20.1 Blinding

The different doses of IP and placebo will be of identical appearance. Only pharmacy personnel will be allowed to see the randomization schedule and know the block size to avoid the possibility of predication by the Investigators and study staff. All study personnel (including the study statistician) will remain blinded to the assignments until the study is completed and the analysis data set is finalized.

20.2 Emergency decoding of blinded treatment

Breaking the code must only be done in emergency situations and should only be used when knowledge of the treatment is necessary for the proper management of the patient. If the treatment code is broken, the reason and the date must be documented. Decoding of the blinded treatment must be reported to the Albireo AB, the CRO Icon and Mayo IRB.

20.3 Prior and concomitant therapy

Rescue medications and other medications considered necessary for the patient's welfare may be given at the discretion of the Investigator.

All concomitant therapy used during and within 30 days of study entry must be recorded in the CRF. No other drug under investigation may be used concomitantly with the study medication.

20.4 Continuation of treatment

Continuation of treatment with the IP after the study period will not be offered.

20.5 Treatment Compliance

Treatment compliance of greater than 80% is required and will be assessed by the patient's record of dosing contained in the Bowel Pattern Diary.

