Within 7-14 days of Visit 1, patients will return to Charlton 7 CRU fasting for the previous eight hours, no food or drink allowed. Vital signs (pulse, blood pressure, respiration rate and temperature) will be measured. They will be given a capsule containing a small amount of In¹¹¹ radioactivity and asked not to eat anything for the next two hours and to return four hours later for one five minute camera picture. Patients will return the following morning at the same time the capsule was taken for one final five minute camera image. If the camera indicates a state of constipation by showing a geometric center at 24 hours to be less than 2.30, , the median of normal colonic transit in normal healthy volunteers (as determined by analysis of a compilation of prior [name] studies ,the patient will continue in the study and be randomized to the study medication. If the camera does not indicate a state of constipation by showing a geometric center equal to or greater than 2.30, the patient will end the study at this time.

Visit 3 Randomization and Administration of Study Medication

The patient will complete a six question survey of constipation symptoms and treatment efficacy at the end of the pre-treatment period, before receiving study medication. The patient will then be randomized to a dose of the study medication which is either a placebo (an inactive substance) or a 15 mg or 20 mg dose of A3309 study medication taken orally once daily for a total of fourteen consecutive days, eleven doses at home and three at the Charlton CRU during the final transit scintigraphy test, Visit 4 to Visit 6. Patients will dose at home and record the dosing of study medication in their Bowel Pattern Diaries.

Prior to Visit 4

Females of child bearing potential must have a negative urine pregnancy test performed within forty-eight hours prior to receipt of radiation in the abbreviated transit scintigraphy test. Females who have experienced a bilateral tubal ligation, hysterectomy or menopause will not need the pregnancy test.

Visit 4 Final Transit Scintigraphy and Pharmacokinetic Sampling

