21.2 Clinical efficacy assessments

1. Gastrointestinal and Colonic Transit

An adaptation of our established scintigraphic method will be used to measure gastrointestinal and colonic transit. Briefly, ¹¹¹In absorbed on activated charcoal particles is delivered to the colon by means of a methacrylate-coated, delayed-release capsule. The capsule is ingested following an overnight fast. Colonic transit measurements will be performed by means of the delayed release capsule. After the capsule emptied from the stomach (documented by its position relative to radioisotopic markers placed on the anterior iliac crests), the study medication is given immediately before a standard radiolabeled breakfast meal is ingested. In this meal, ^{99m}Tc-sulfur colloid is used to label two scrambled eggs that will be eaten with one slice of whole wheat bread and one glass of skim milk. This meal facilitates measurement of gastric and small bowel transit.

Relative to the time of consumption of breakfast meal, abdominal camera images are initially obtained every 30 minutes for the first two hours, then hourly for the next six hours. At about 4 hours, a standard chicken breast lunch will be given. Camera images will be taken at 5, 6, and at 8 hours post breakfast meal. At about 8 hours, the standard roast beef sandwich snack will be given. The patient will leave the CRU after the completion of the 8 hour image and will return the following two mornings in order to receive study medication and obtain 24 and 48 hour scans fifteen minutes later. The performance characteristics of this test are summarized elsewhere. Please see relevant references on the methods (29,30).

2. Assessment of stool frequency and consistency

During the study, patients will complete a daily Bowel Pattern Diary to record their bowel habits. The Bowel Pattern Diary will be dispensed at Visit 1 and will be collected at the completion of the study at Visit 7.

- 3. Pharmacokinetic (PK) and pharmacodynamic (PD) assessments
- a. Sample collection and handling

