24.2 Analysis data sets

The primary analyses will follow the intent to treat (ITT) paradigm with all patients randomized included in the analyses. Those patients with missing response values will have their missing values imputed via the overall (patients with non-missing data) mean and a corresponding adjustment in the ANCOVA residual error variance degrees of freedom (subtracting one for each missing value imputed). A per protocol analysis of transit data will also be performed. The per protocol population consists of all patients having at least 80 % compliance with study drug and having participated in the transit evaluation.

Safety data will be presented for all patients receiving investigational product.

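### For the 11 home doses, the compliance figure that defines the per protocol transit population comes from the diary alone, and the product reconciliation in 19.3 is not linked to it

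*Combined protocol and SAP*

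**What the plan says.** - **Compliance rule (20.5).** "Treatment compliance of greater than 80% is required"; compliance "will be assessed by the patient's record of dosing contained in the Bowel Pattern Diary". No other source is named.
- **Use of the rule (24.2).** The per protocol population for transit is "all patients having at least 80 % compliance with study drug and having participated in the transit evaluation". The primary analysis is ITT and includes all randomized patients.
- **Where doses are taken (11.3, Visit 3, and 19.2).** Eleven doses are taken at home and three at the CRU, where nurses give them. For the home part: "Patients will dose at home and record the dosing of study medication in their Bowel Pattern Diaries".
- **The diary (21.2 and 34.5).** "The Bowel Pattern Diary will be dispensed at Visit 1 and will be collected at the completion of the study at Visit 7". The daily form has one dosing field, the clock time at which medication was taken. It has no entry for tablets or sachets.
- **Accountability (19.3).** "The IP will be stored at and dispensed by the Mayo Research Pharmacy and administered by the Charlton 7 CRU nurses". The pharmacy records stock, product prepared for the CRU and unused product coming back from the CRU, and differences must be explained. The CRU records what it administers. The Monitor accounts for unused product, and 23.1 repeats that check.
- **Supply (19.1).** The patient-numbered container is labelled "18 sachets containing two tablets each". Its label says to take one sachet daily before breakfast. It gives no last day and does not mention the CRU days.

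**The concern.** Per protocol status is decided mainly by doses that nobody observes, and the only named evidence for them is the patient's own entry of a time. Each dose is two tablets, so a diary entry cannot show whether a full sachet was taken.

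The plan already requires product to be reconciled, and that would be a more objective source. As written, though, 19.3 follows product between the pharmacy and the CRU and does not fit a trial with 11 home doses. It does not say that patients bring anything back, when a count would be made, or that a count would feed the compliance percentage.

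The per protocol transit analysis is the only one that selects on compliance. If patients on active drug over-report home dosing, under-dosed patients stay in that analysis and both dose contrasts would tend to shrink. No planned measurement fills the gap. Section 8.1 expects a half-life below 4 hours, and 8.8 reports no detectable drug 24 hours after dosing in the earlier patient study. The pre-dose sample at Visit 4 therefore says little about days 1 to 11.

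**Working it through.** **Inputs.** Home doses 11 and CRU doses 3 (11.3, 19.2); sachets per container 18, two tablets each (19.1); compliance threshold 80% (20.5, 24.2); planned patients per arm 12 (24.9).

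**1. The plan's own total.** 11 + 3 = 14 doses, as stated.

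**2. What the 80% rule means in doses.** 0.80 × 14 = 11.2, so the smallest passing number is 12.
- 11/14 = 78.6%, fails.
- 12/14 = 85.7%, passes.

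Section 20.5 asks for more than 80% and 24.2 for at least 80%. No whole number of doses out of 14 equals exactly 80%, so both wordings give the same cut.

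**3. Share of the evidence that is self-report.** CRU doses are 3/14 = 21.4% and home doses 11/14 = 78.6%. If all three CRU doses are taken, the patient needs 12 − 3 = 9 of 11 home doses (9/11 = 81.8%). She must miss at least three home doses before misreporting can change her status.

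**4. Supply against schedule.** 18 − 14 = 4 sachets more than the schedule uses (36 tablets against 28). If the whole container goes home, which the documents do not state, a patient with all 11 home doses arrives at Visit 4 with 18 − 11 = 7 full sachets. At the limit of 9 home doses she arrives with 18 − 9 = 9. So 10 or more full sachets would indicate failure of the rule, and a count at Visit 4 could decide status.

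**5. Size of one misclassification.** One patient is 1/12 = 8.3% of an arm, if all 12 are in the per protocol set. As an upper bound, suppose one active-arm patient had no drug effect at all and the other 11 had mean effect Δ. The arm's mean effect would be (11/12)Δ, a loss of 8.3%. The real loss would probably be smaller, because even a patient who skipped home doses receives nurse-given drug during the transit test.

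**6. Passages side by side.** 19.3 has CRU nurses administering the product, while 11.3 and 19.2 have 11 doses taken at home. The 19.1 label gives an open-ended daily instruction, 11.3 gives 11 home plus 3 CRU doses, and 22.7 allows no more than one dose per calendar day. These texts are not aligned with one another.

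**The case against.** The strongest reply is that the plan has more safeguards than 20.5 suggests, and that little depends on compliance.

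- **Some doses are observed and product is reconciled.** Three of 14 doses are nurse-given and recorded, and 19.3 and 23.1 require reconciliation and Monitor accountability. This stands. A reader might infer that no count of product exists anywhere, and the documents do not support that. The gap is that the count is not linked to compliance and no patient return of home supply is described.
- **The primary analysis is ITT.** This stands. A reader might infer that the main result is at risk, but compliance enters only the per protocol transit analysis.
- **Spare sachets.** A reader might infer doubled doses on CRU days, or dosing past day 14 that would disturb the Visit 7 C4, lipid and PK samples. The documents do not support this. They do not say that all 18 sachets go home or whether CRU doses come from the same container. Section 22.7 limits intake to one dose per calendar day. The coordinator reviews instructions with patients, and neither those instructions nor the consent form is in the file.
- **Half-taken sachets.** A reader might infer that a 20 mg patient could fall below the 15 mg arm by taking one tablet. Tablet strength is not given, and both labels say to take both tablets.
- **A count is also indirect.** True: a missing tablet is not proof of intake. A count can still contradict a diary, whereas the diary as designed has nothing to check it against.

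**Conclusion.** The point holds for the 11 home doses. Their contribution to the compliance percentage comes only from a diary that records a time. Section 19.3 is written for CRU dosing and has no link to the 80% rule in 20.5 and 24.2.

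The size is modest. The per protocol transit set alone is affected, each misclassified patient is 8.3% of a full arm, and only patients who miss three or more home doses can be misclassified, assuming all CRU doses are taken. The documents give no over-reporting rate, so the expected dilution cannot be stated beyond the one-patient bound. Late return of the diary at Visit 7 does not itself bias the percentage, but it means that no check is planned before the transit test.

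The change is worth making because it is cheap and uses reconciliation that the plan already requires. The plan's main conclusion does not depend on it.

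**What to change.** Amend 19.3, 20.5 and 24.2 together.

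1. **19.3:** cover the home supply. Patients return the container with used and unused sachets at an existing visit, for example Visit 4, and staff count and record sachets and tablets.
2. **20.5 and 24.2:** compute compliance from that count plus the CRU administration record, with the diary as a cross-check and a stated rule for disagreement. Use one wording of the threshold; the choice does not change the cut of 12 doses.
3. **Supply:** state whether the whole 18-sachet container goes home, since the expected 7 full sachets at Visit 4 depends on that.
4. **Label and schedule:** reconcile the 19.1 label with the 11 home plus 3 CRU doses in 11.3 and the one-dose-per-day text in 22.7. The sponsor and investigator should decide how doses are supplied and what patients are told.

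The cost is a few minutes of counting at a planned visit, one CRF line and an amendment to the wording. No extra visit, procedure or patient is needed. The downside is that a few patients may leave the per protocol set.
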